#### A3a. Financial Conflict of Interest

Does any member of study personnel (Investigator (including investigator's spouse and/or dependent children)) that are involved in the design, conduct, or reporting of the research have a Significant Financial Interest (SFI) that would reasonably appear to be affected by the research for which funding is sought and/or associated with an entity/business that would reasonably appear to be affected by the research?

No

#### **A5. Funding Source:**

Organization: NATIONAL INSTITUTE OF DIABETES AND DIGESTIVE AND KIDNEY DISEASES (NIDDK)

#### **A6b. Research conducted outside of the United States:**

Country:  
Facility/Institution:  
Contact/Investigator:  
Phone Number:

If documentation of assurances has not been sent to the Office of Research, please explain:

#### **A7. Research Category:**

#### **A8. Therapeutic Intent**

Does this trial have therapeutic intent?

No

#### **A9. ClinicalTrials.gov Registration**

Does this protocol/trial require registration on ClinicalTrials.gov due to it: meeting the definition of an Applicable Clinical Trial, being required under the terms and conditions of an award, or being proposed to be published in ICMJE journals?

Yes

Who will be responsible for registering and maintaining the registration of this Applicable Clinical Trial?

The BCM PI will register the trial because either:

- the trial is BCM PI-initiated,
- BCM is the lead site of this multicenter trial, or,
- the industry sponsor has instructed the BCM PI to register the trial, or,
- registration of this trial is required as a term and condition of the award by the funding agency.

ClinicalTrials.gov Identifier:

NCT04953442

#### **Section B: Exempt Request**

##### **B. Exempt From IRB Review**

Not Applicable

## Section C: Background Information

Hispanic adolescents are disproportionately burdened by obesity (25.8% vs 18.5% general population) and type 2 diabetes (T2D) compared to non-Hispanic white youth. Disparities in T2D emerge early in life and are driven in part by unhealthy lifestyle behaviors including low levels of physical activity (PA), excessive time spent in sedentary behaviors (SB), and short sleep durations. Given that Hispanic youth are the fastest growing pediatric subgroup in the U.S., developing strategies to promote healthy lifestyle behaviors and addressing T2D disparities is a public health imperative. Wearable activity monitoring devices like Fitbits are designed to continuously monitor both wake time and sleep behaviors. Studies using wearable devices in conjunction with text-messaging or smartphone applications have been effective in increasing PA in adults; however, less is known about the use of these technology-based tools among adolescents, particularly among high-risk youth like Hispanic adolescents. Therefore the purpose of this study is to examine the feasibility, acceptability, and preliminary efficacy of a technology-based intervention that uses a Fitbit and text messages grounded in the Self-Determination Theory to promote healthy lifestyle habits and reduce risk for type 2 diabetes among a sample of Hispanic adolescents (14-16 years) with obesity.

## Section D: Purpose and Objectives

The purpose of this study is to examine the feasibility of a 12-week goal-setting intervention that utilizes a Fitbit device and text messages grounded in the Self-Determination Theory (SDT) to promote healthy wake time (PA,SB) and sleep behaviors in Hispanic adolescents (14-16 years old) with obesity (BMI%≥95th).

## Section E: Protocol Risks/Subjects

### E1. Risk Category

Category 1: Research not involving greater than minimum risk.

### E2. Subjects

Gender:

Both

Age:

Adolescent (13-17 yrs)

Ethnicity:

Hispanic Or Latino

Primary Language:

English, Spanish

Groups to be recruited will include:

Healthy, non-patient, normals

Which if any of the following vulnerable populations will be recruited as subjects?

Children

Vulnerable populations require special protections. How will you obtain informed consent, protect subject confidentiality, and prevent undue coercion?

Informed consent will be obtained from parents of participating adolescents and child assent will be obtained from participating adolescents. Consent and assent will be obtained electronically by a trained research staff member. In this study, qualitative interviews will be conducted remotely, thus an electronic consent/assent will be sent to the participant via REDCap, we will schedule a time and day to speak to the participant and his/her parent or legal guardian, at which time we will review the forms over the phone and answer any questions, and then the participant and his/her parent or legal guardian will electronically sign the consent form and send it back to the research team. For participation in the intervention, the participant and his/her legal guardian will complete the electronic consent/assent form in person. The research staff member will explain all aspects of the study and answer any questions. Whether the participant is completing the consent/assent forms remotely or in person, we will ask comprehension questions to ensure that parents and adolescents understand all study procedures, risks, benefits, and the voluntary nature of this study. We will also provide all participants and parents or legal guardians with a paper copy of the consent and assent forms for their personal records.

### E3. Pregnant woman/fetus

Will pregnant women and/or fetuses (as described in 45 CFR 46 Subpart B) be enrolled in the research?

No

#### **E4. Neonates**

Will neonates of uncertain viability or nonviable neonates (as described in 45 CFR 46 Subpart B) be enrolled in the research?

No

#### **E5. Children**

Will children be enrolled in the research?

Yes

### **Section F: Design/Procedure**

#### **F1. Design**

Select one category that most adequately describes your research:

c) Pilot

Discuss the research design including but not limited to such issues as: probability of group assignment, potential for subject to be randomized to placebo group, use of control subjects, etc.

In collaboration with Hispanic youth (N=30) and an expert panel (N=6), text message content will be adapted and refined from a previously conducted pilot study. A mixed-methods approach (surveys and interviews) will be applied to ensure that text message content adheres to the SDT and is age and culturally appropriate. A different sample of Hispanic youth (N=48) will be recruited and randomized to the intervention or a wait-list control group. In the intervention, the youth will receive guidance from the research team on setting weekly steps/day and hours of sleep/night goals, a Fitbit device to self-monitor progress towards goals, and theory-informed text messages that promote autonomous motivation for behavior change. At the end of the initial 12-week intervention, youth in the wait-list control group will be invited to participate in the intervention. Feasibility will be evaluated using a priori criteria for recruitment, data collection, intervention implementation, and acceptability.

This study will receive assistance from a non-BCM personnel, [name], will assist with the development of project materials, assist with data collection and the implementation of the intervention. [name] will also assist in conducting literature reviews and assisting in the lab in basic scholarly work such as creating data tables. [name] will rely on the BCM IRB for her involvement in this research.

Inclusion Criteria:

Participants will be screened using the following inclusion criteria: 1) Self-report as Hispanic 2) obese, defined as body mass index percentile (BMI%)  $\geq$  95th percentile 3) between the ages of 14-16 years, and 4) own his or her own cellphone.

Exclusion Criteria:

Youth will be excluded based on the following criteria: 1) Taking a medication (i.e. steroids) or diagnosed with a condition (i.e. sleep apnea) that influences activity, sleep, and/or cognition, 2) recent hospitalization or injury that prevents normal physical activity, 3) pregnant, and 4) currently enrolled in an exercise program or currently using a personal activity monitoring device like Fitbit.

#### **F2. Procedure**

Hispanic adolescents (N=30) will participate in in-depth interviews. Trained interviewers will use an interview script to elicit information on: 1) personal values, 2) given that social frameworks have demonstrated that multiple levels of influence affect health behaviors in high-risk, minority youth we will ask questions as to how to promote wake-time and sleep behaviors in a manner that is feasible and realistic in the environmental and sociocultural context of Hispanic youth, 3) the type of goal-setting guidance and feedback desired, and 4) desired frequency and timing of text messages. To protect staff and participants, we will conduct interviews via zoom until it is safe to host interviews in person. In-depth interviews will be audio-recorded, transcribed, coded by two trained, independent coders, and qualitatively analyzed using NVivo version 9. Thematic content analysis will be used to identify emergent themes to adapt existing text messages. As youth are screened and participate in interviews, parents will complete a text-based survey, to assess their perceptions of the intervention.

An expert panel (N=6) of co-investigators ([name], [name], [name], [name]) and consultants ([name], [name]) will convene to ensure text messages are age and culturally-appropriate, adhere to the self-determination theory, and use evidence-based strategies to promote healthy behaviors. Consultants will not participate in any data collection or seek IRB Approval from their home institutions. Youth that participated in the interviews will review a revised draft of the text messages and provide feedback via a survey. If extensive modifications are needed an additional review by youth and the expert panel will be conducted.

To test the feasibility and acceptability of the intervention, we will recruit a new sample of Hispanic adolescents (14-16 years) with obesity. Youth will be randomized (1:1) to the intervention or wait-list control.

**Intervention** In the intervention, youth will be given a Fitbit which has shown high validity and reliability (ICC 0.71 - 1.00) for assessing steps/day and sleep in youth. Participants will download the Fitbit app and staff will input individual user height and weight to improve measurement accuracy. The theory-informed text messages that were previously developed with youth and the expert panel will be sent 3-5 times/week using a text-message platform called Mosio, which is HIPAA compliant and secure. We have exacted a Business Associate Agreement with Mosio. At the start of the week, texts will guide participants to set one activity and one sleep goal. Texts will promote autonomy by encouraging youth to develop their own solutions for achieving their goals. Mid-week texts will emphasize competence, acknowledge progression towards goals, and provide tips and evidence-based strategies for increasing health behaviors (competence). Tips and strategies for increasing physical activity will include suggestions on resources within each participant's neighborhood, which will require the use of their home address. End-of-week texts will provide feedback on goal achievement and encourage participants to connect goal achievement to personal values to build relatedness.

Youth in the intervention will also receive assistance in goal-setting as well as need supportive feedback on goal attainment. At the start of week 2, research staff will contact participants via text message to guide them in setting goals for steps/day and hours of sleep/night based on their weekly averages from the previous week. In successive weeks, participants will be guided to gradually increase their step count and sleep goals to meet or maintain current recommendations of ~12,000 steps/day and 8-10 hours of sleep/night. Participants with less than 5,000 steps/day will be guided to increase their average by 600 steps/day each week, participants with 5,000-11,999 steps/day will be guided to increase their steps/day goal by 10% of their week 1 average in successive weeks, and participants with greater or equal to 12,000 steps/day or greater will be instructed to maintain that level of step counts in successive weeks. Achieving greater or equal to 12,000 steps/day is equivalent to meeting PA recommendations of 60 minutes of PA/day. For sleep, participants that average less than 8 hours of sleep/night will be encouraged to increase their average sleep time by 30 minutes each week and participants with more than 8 hours of sleep/night will be encouraged to maintain that sleep duration. Data collected using the Fitbit Flex is continuously collected and wirelessly transmitted to a web-based platform called Fitabase. This secure, platform aggregates and analyzes step and sleep data at the daily, weekly, and monthly level, and provides customized data reports for each participant. These reports will be downloaded and saved for data checks and goal monitoring. These reports will inform help us develop texts that guide goal-setting and provide feedback on goal achievement.

At the completion of the intervention, youth will return the Fitbit Flex to the study team.

**Wait-list Control Group** Youth in the wait-list control group will also receive a Fitbit and a one-page handout with standard health information on the importance of PA and sleep to their health. After the 12-week intervention period, youth in the wait-list control group will be invited to participate in the intervention.

**Assessments Primary Outcomes:** Feasibility will be evaluated using a priori criteria: recruitment, data collection, the integrity of the study protocol, technical issues, internal consistency of measures, and satisfaction. Given this study's high potential for dissemination in clinical settings, 'Recruitment' and 'Data Collection' criteria will assess the feasibility of recruiting and retaining participants from community clinics. 'Integrity of Study Protocol' criteria will be used to identify the feasible and acceptable 'dose' of the intervention. 'Technical Issues' criteria will assess the feasibility of using the Fitbit device and text messaging as behavior change tools. 'Internal Consistency of Measures' criteria will assess the appropriateness of our instruments for Hispanic youth. 'Satisfaction' will assess acceptability, which is especially important for interventions in minority populations. This will provide information on the availability of high-risk youth in community clinics and the ability of our recruitment strategies to engage youth from these settings.

**Secondary outcomes:** Physical activity, sedentary behaviors, and sleep will be assessed using a hip-worn wGT3X-BT accelerometer (Actigraph, Pensacola, Florida). Participants will wear the accelerometer 24 hours a day for 7 days at both timepoints. A research team member will review instructions for device wear and will send daily text messages to remind participants to wear the device to promote compliance. Accelerometer data will be processed using ActiLife v6.13 software. A valid day of wear will be defined as  $\geq 18$  hours of wear on 4 days or more, one of which has to be a weekend day. Evenson cut points will be used to analyze and categorize SB (defined as <100 counts per minute) and moderate-to-vigorous PA. The Sadeh algorithm will be used to assess sleep duration. While wrist-worn devices are superior for assessing all sleep characteristics (i.e. sleep efficiency, wake after sleep onset, etc), hip-worn devices provide accurate measures of sleep duration and timing. Participants will be asked to complete a wear log to indicate wake and sleep times, which will be used to verify accelerometer data. Data will be reported as average minutes per day spent in PA, SB, and sleep.

**Tertiary Outcomes:** Height and weight will be measured to the nearest 0.1cm and 0.1 kg, using a portable stadiometer and research scale to calculate BMI percentile. We will assess waist circumference to measure central adiposity. Psychological Needs will be assessed using the Psychological Need Satisfaction in Exercise Scale (18-items), which has shown acceptable validity and reliability among youth. Autonomous motivation for PA will be assessed using a scale from the Behavioral Regulation in Exercise Questionnaire-2 (23-items), which has acceptable psychometric properties among youth. Each participant's social network will be assessed using the interview-administered social network survey to analyze the social connections or ties of each participant in preparation for the next version of this study, which will allow participants to participate and receive support from family members or friends. Information collected via the social network survey will be used to calculate descriptive information on the number of ties the participant reports and the strength of those ties, which will give us an overall measure of how weak or strong their social network is. This data will be unidentified and aggregated. We will only collect first names and will never collect the address, phone number, or any other personal

health information on any of the network ties reported by participants. There will be no attempts to identify or collect data from any of the ties mentioned by participants.

Process Evaluation data will be collected to further evaluate the feasibility, assess the impact of implementation on study outcomes, and identify mechanisms by which the intervention impacts health behaviors and BMI. We will use research team logs and field notes entered into a REDCap online database to assess the recruitment of participants, resources needed for intervention implementation, maintenance of the participants, implementation fidelity, the dose of intervention delivered and received, and potential contamination.

All assessments will be conducted in a private room at a community center partners like Baker Ripley or at the home of the participant. For safety, trained research assistants will travel in pairs for home-based data collection. They will notify their supervisor [name] of their time of arrival and departure at the participant's home. Additionally, we will provide reimbursement for use of uber or other ride-share services.

**Exit-Interviews.** A subsample of participants (N=15) randomized to the intervention will participate in a 1-hour, post-intervention exit interview

Data collection for this study has been concluded. The current database includes N=43 participants. To conduct further analysis and maximize the potential knowledge to be gained from this study we will collaborate with students and faculty at Rice University through the Data 2 Knowledge capstone program to conduct high-level analysis to identify patterns of 24-hour physical activity and sleep behaviors and their associations with metabolic health. Data shared through this capstone program will be de-identified and will include demographic information, accelerometer derived physical activity, sleep, and sedentary behaviors, anthropometrics (BMI, height, weight, waist circumference), zipcode (not full address) as well as surveys on autonomous motivation. An IRB protocol will be submitted at Rice University and all faculty and students working on this project will be added to the IRB protocol at Rice University.

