3.1 Study Aims

Aim 1. Use a mixed-methods approach (in-depth interviews and surveys) to adapt and refine SDT-informed text message content for Hispanic adolescents.

Aim 2. Test the feasibility of a 12-week goal-setting intervention utilizing a Fitbit and SDT-informed text messaging for improving PA, SB, and sleep, in Hispanic adolescents with obesity.

Aim 2 Hypothesis: This approach will satisfy all a priori feasibility criteria for recruitment, data collection, integrity of the study protocol, internal consistency of measures, technical issues, and satisfaction.

Aim 3. Use in-depth exit interviews to further examine the feasibility and acceptability of the intervention.

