3.2 Primary outcome (Aim 2)

Feasibility is the primary outcome and will be evaluated for the development of a larger trial using the following a priori feasibility criteria:^{1,2}

1. **Recruitment:** Recruit and enroll 48 Hispanic adolescents 14-16 years of age with obesity from community clinic settings.
2. **Data Collection:** Collect data on 100% of participants at baseline and 85% of participants at post-intervention.
3. **Integrity of Study Protocol:** Participants wear their Fitbit device for ≥ 5 days/week and respond to 80% of text messages when prompted throughout the 12-week intervention.
4. **Internal Consistency of Measures:** Cronbach's alpha for survey scales ≥ 0.7 .
5. **Technical Issues:** $\leq 10\%$ technical issues with the transmission and receipt of text messages or Fitbit device functioning.
6. **Satisfaction:** $\geq 80\%$ report 'excellent' – 'good' satisfaction with the intervention.

'Recruitment' and 'Data Collection' criteria will assess the feasibility of recruiting and retaining participants from community clinics.³ We will record the number of participants that are screened, enrolled, and the time and resources that it takes to complete recruitment activities and reach our recruitment goal (N=48). This data will provide information on the availability of eligible, high-risk youth in partnering clinics and the ability for our recruitment strategies to engage youth from these

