settings.² This data will also provide preliminary insight on the feasibility of recruiting and disseminating this intervention in community clinic settings in future studies. 'Integrity of Study Protocol' criteria will be used to identify the feasible and acceptable 'dose' of the intervention.^{1,3,4} We will use the Fitabase online platform to record the number of days per week in which youth wear the Fitbit device during the intervention. We will also use the Survey Signal text messaging service to record the number of times that each participant responds to text messages when prompted during the intervention. This data will provide information on the feasibility and acceptability of asking youth to wear an activity monitoring device and respond to intervention text messages over a 12-week period. 'Technical Issues' criteria will be used to assess the feasibility of using a Fitbit device and text messaging as behaviour change tools. Delivering the intervention with limited technical issues will ensure that these technology components are capable of delivering behavioural interventions with a high degree of fidelity. 'Internal Consistency of Measures' criteria will assess the appropriateness of our survey instruments for use in a population of Hispanic youth at high-risk for type 2 diabetes.^{1,3} Last, 'Satisfaction' will assess acceptability,³ which is especially important for interventions in minority populations.⁵ A survey will be used to assess the degree to which participants found the intervention, including the device, text message content, and the frequency and timing of text messages acceptable.

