3.4 Tertiary Outcomes (Aim 2)

Percentage over the 95th percentile in body mass index (BMI)

Psychological needs (Psychological Need Satisfaction in Exercise Scale), and autonomous motivation (Behavioural Regulation in Exercise Questionnaire-2).

4 Study Design

To address the research question, "**Is a technology-based intervention that promotes PA, SB, and sleep, feasible among Hispanic adolescents with obesity?**" a two-armed, pre-post design will be used to test the feasibility of the intervention compared to a wait-list control group. Limitations of previous studies include the absence of control groups.^{6,7} A wait-list control comparison is appropriate for studies in the pre-efficacy phase that aim to assess feasibility.⁸ Another limitation of previous studies is the use of self-reported measures to assess health behaviors.⁹⁻¹¹ We will rely solely on research grade accelerometers to objectively measure wake time and sleep behaviors at baseline (T0) and 12- weeks post-intervention. Following baseline assessments, youth will be randomized in a 1:1 ratio to the intervention or wait-list control using a computerized random number generator in SAS version 9.4 (SAS Institute, INC., Cary, NC). After the 12-week study period, youth in the wait-list control group will be invited to participate in the intervention. A subsample of youth (N=15) initially randomized to the intervention will be invited to participate in an exit in-depth interview.

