5.1 General Considerations

Analyses will be conducted on all subjects based on the treatment group assigned (intervention or wait-list control) according to the intent-to-treat principal. All statistical tests will be 2-sided and performed using a 5% significance level, leading to 95% (2-sided) confidence intervals. Variables will be summarized overall and by treatment group (intervention, wait-list control). Continuous variables will be described using number of subjects, mean, standard deviation, median, 25th percentile, 75th percentile, minimum, and maximum. Skewness, kurtosis, tests for location and histograms will be examined to assess normality and the need for variable transformations. Bivariate continuous variables will be depicted using scatterplots and the Spearman correlation coefficient. Categorical variables will be described using number of subjects and percentages. Denominators of percentage calculations will be based on the number of subjects in the treatment group (intervention or wait-list control).

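### Does the Fitbit given to wait-list controls leave feasibility criteria 3 and 5 open to scoring on one arm or on two?

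*Protocol*

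**What the plan says.** Under the wait-list control heading, Protocol F2 states: "Youth in the wait-list control group will also receive a Fitbit and a one-page handout with standard health information". It does not say when controls receive the device, whether they are asked to wear it, or whether it is linked to Fitabase. The app set-up and the Fitabase reports are described only in the text on the intervention.

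SAP 3.2 lists six feasibility criteria. Criterion 3 reads "Participants wear their Fitbit device for ≥ 5 days/week and respond to 80% of text messages when prompted" over the 12 weeks. Criterion 5 allows at most 10% "technical issues with the transmission and receipt of text messages or Fitbit device functioning". Neither names an arm. The explanation after the list says that staff will use Fitabase to "record the number of days per week in which youth wear the Fitbit device during the intervention".

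SAP 4 describes "a two-armed, pre-post design will be used to test the feasibility of the intervention compared to a wait-list control group" and does not mention a control device. SAP 5.1 gives the general reporting rules: "Variables will be summarized overall and by treatment group (intervention, wait-list control)" and "Denominators of percentage calculations will be based on the number of subjects in the treatment group (intervention or wait-list control)". The remaining subsections of SAP 5 cover missing data, the Aim 1 interviews, and the secondary and tertiary outcomes. None is devoted to the primary outcome. The Aim 2 hypothesis in SAP 3.1 is that "This approach will satisfy all a priori feasibility criteria".

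**The concern.** If controls hold a Fitbit during the 12 weeks, both arms can produce wear data and device faults. SAP 5.1 would then give an intervention, a control and an overall figure for each, and no sentence says which one is compared with the threshold.

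The choice could matter. Controls get no intervention texts, so they can add device faults but no text faults, and pooling may dilute the fault rate of the arm that received the full package. Controls also have no goals to track, so their wear may be lower and could pull an overall wear figure under 5 days per week. Because the hypothesis requires every criterion to be met, one criterion changing sides would change the primary conclusion. Protocol F2 also reports that data collection has ended, so a population left unstated might be chosen with the data in view.

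**Working it through.** **Can the criterion 5 verdict flip?** Inputs: 48 youth (Protocol G1, SAP 3.2), 1:1 allocation (Protocol F2, SAP 4), so 48/2 = 24 per arm, and a 10% limit (SAP 3.2). Assumption: the unit is a participant with at least one fault. The SAP gives no unit.

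Largest passing count = floor(0.10 × n):

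- Intervention arm, n = 24: floor(2.4) = 2. Two is 2/24 = 8.3% (pass); three is 3/24 = 12.5% (fail).
- Both arms, n = 48: floor(4.8) = 4. Four is 4/48 = 8.3% (pass); five is 5/48 = 10.4% (fail).

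So 3 intervention and 1 control fault fail on one arm and pass pooled. Two and 3 pass on one arm (8.3%) and fail pooled (10.4%). A flip is possible in either direction.

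**How often?** Let X ~ Bin(24, p1) be the intervention faults and Y ~ Bin(24, p0) the control faults. Disagreement is the probability that exactly one of X ≤ 2 and X + Y ≤ 4 holds. Every rate below is assumed.

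| p1 (intervention) | p0 (control) | Opposite verdicts |
|---|---|---|
| 2% | 2% | 1.2% |
| 5% | 5% | 10% |
| 10% | 10% | 25% |
| 20% | 20% | 10% |
| 10% | 2% | 29% |
| 15% | 2% | 34% |
| 20% | 5% | 17% |
| 5% | 15% | 44% |
| 30% | 10% | 1.9% |
| 40% | 5% | 0.5% |

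Among these scenarios, disagreement is substantial when one arm's rate or the pooled rate lies near the 10% limit, and small when both lie well to one side of it.

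**Can the wear half of criterion 3 flip?** Only under an invented scoring rule, since the SAP does not say whether the 5 days applies to a mean or to a share of participants. Scored as a mean with equal arms, the overall mean is below 5 when the control mean is below 10 minus the intervention mean. For an intervention mean of 5.5 the cut is 10 − 5.5 = 4.5.

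**Which reading does the text support?**

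- *Criterion 3.* Wear is joined by *and* to answering prompted texts. Controls receive no intervention texts in those 12 weeks, so they cannot meet the joint criterion. SAP 3.2 gives its purpose as finding a workable dose of the intervention and counts wear in that period ("record the number of days per week in which youth wear the Fitbit device during the intervention").
- *Criterion 5.* SAP 3.2 justifies it by the need to deliver the intervention faithfully through these technologies. Protocol F2 says it assesses the device and the texts as tools for changing behaviour. Protocol G2 defines fidelity and dose by wear, number of technical issues and text engagement together. All three concern the arm receiving the intervention.
- *SAP 4.* Testing feasibility against a control group keeps the arms apart and gives no support for pooling.
- *SAP 5.1.* This is a general descriptive rule. Its percentage denominator is the treatment group, which gives 24 and not 48. Only the word *overall* in the summary rule points to a pooled figure, and that rule sets no population for a pass/fail threshold.

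**The case for a change.** The best case for a change is that the criteria are pass/fail, the word *participants* in criterion 3 is unqualified, and for criterion 5 the explanatory text leans to the intervention arm without excluding control devices. A sentence naming the arm would cost almost nothing and would remove any suspicion of a choice made after seeing the data. Naming the comparator in SAP 4 would also tell readers that, if controls had the device during the 12 weeks, the secondary contrast is against Fitbit plus handout.

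The textual facts stand: the SAP is silent on the control Fitbit, and neither criterion line names an arm. So does the arithmetic, under its assumptions. The rest carries less weight:

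- The sentence would record the reading that the rationale already gives, so the verdict would be the same with or without it.
- Nothing shows that control device data exist in a form that could be pooled.
- The suspicion of a late choice cannot be tested, because the documents as supplied do not show when the SAP was fixed relative to analysis.
- Protocol F2 reports a database of 43. If that is the number randomised, criterion 1 (48 enrolled) has already failed, and a flip in criterion 5 could not rescue the claim that all criteria are met. If it is not, it gives no basis for working with 43.
- The comparator is stated in Protocol F2, and repeating it in SAP 4 alters no test or estimate.

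The missing unit for criterion 5 and the missing pass line for criterion 3 are real gaps, but they are separate from the arm question and naming an arm would not close them.

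**Conclusion.** The concern does not call for a change. The omission is real but is missing detail that an analyst following the plan would fill sensibly. Criterion 3 can be met only by youth who receive the texts, and criterion 5 is explained throughout as a check on delivering the intervention. Both would be scored on the intervention arm, with any control-arm device data shown descriptively under SAP 5.1.

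If someone did pool the arms, the criterion 5 verdict could differ, as in 12.5% against 8.3%. In the scenarios tabulated, the probability of opposite verdicts runs from 0.5% to 44%. That range rests on assumed fault rates, a participant-level unit, 24 per arm and control device data being recorded, none of which the documents confirm except the planned 24 per arm. For criterion 3, no flip can be shown without inventing a pass line.
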